4.2 Study Period

The study start date will be the earliest EUA date for vaccination for each age group:

- BNT162b2
 - o Age 6 months-4 years: June 17th, 2022
 - o Age 5-11 years: October 29th, 2021
 - o Age 12-15 years: May 10th, 2021
 - Age 16-17 years: December 11th, 2020
- mRNA-1273:
 - o Age 6 months-17 years: June 17th, 2022
- NVX-CoV2373:
 - o Age 12-17 years: August 19th, 2022

Surveillance will continue through a pre-specified surveillance length, set for each AESI and age group to the number of events expected to be observed in the 6-month period from initiation of surveillance based on the incidence of the event estimated from historical data as well as the anticipated number of vaccine doses administered in the study population in this time period. The study period may be adjusted if additional vaccines for the pediatric population are approved.

4.3 Exposure

The exposure will be defined as receipt of any dose(s), including the primary series doses and the third/monovalent booster dose, ¹ of the BNT162b2 COVID-19, mRNA-1273, or NVX-CoV2373 pediatric vaccines or other future COVID-19 vaccines available for the pediatric population in US. Bivalent booster doses will be excluded from this analysis and will be evaluated in a separate analysis. Vaccinations will be identified in administrative claims data through product codes such as Current Procedural Terminology (CPT)/Healthcare Common Procedure Coding System (HCPCS) codes or National Drug Codes (NDCs) in the professional, outpatient institutional, inpatient, or prescription drug care settings, and will be identified through product codes such as CVX (vaccine administered) codes in IIS data. The list of valid codes will be continuously reviewed. The primary analysis will test for an increased risk of each AESI for primary series, and the secondary analysis will focus on increased risk of AESI following specific doses (e.g., Dose 1, Dose 2, and boosters/third doses separately).²

4.4 Outcomes

A list of pre-specified potential AESI following COVID-19 vaccine administration in the pediatric population is included in Table 3 AESI pre-specified for descriptive and sequential testing are labeled as analysis type "Rapid Cycle Analysis (RCA) and Descriptive," and those pre-specified for descriptive monitoring only are noted "Descriptive Only". The classification of outcomes into those to be monitored descriptively and those monitored via sequential testing is based on the availability of estimable background rates for the outcomes and the expected frequency of events. This list of AESI may be updated based on observed adverse events in pre-licensure trials, adverse events reporting from other surveillance sources or other sources including international regulators.

Table 3. AESI, Age Groups, Settings, Clean Windows, Risk Windows, and Analysis Type for the Pediatric Population

AESI	Setting	Clean Window	Risk Window	Age Groups of Interest	Descriptive Monitoring	Sequential Testing
		Po	ediatric Outcome	2S		
Acute Myocardial	IP	365 days*	1-28 days [40, 41]	6 m-4 y, 6 m-5 y	Yes	No
Infarction		,	,	5-17 y, 6-17 y	Yes	No

¹ For BNT162b2 in ages 5-17 and mRNA-1273, the primary series is defined as doses 1 and 2. For BNT162b2 ages 6 months – 4 years, the primary series is defined as doses 1, 2 and 3. For NVX-CoV2373, the primary series is defined as doses 1 and 2 in ages 12-17 years.

² Dose assignment is based on the chronological order in which vaccinations are observed for the person, i.e., the first vaccination observed for a person is assigned a dose number of 1, the second vaccination observed is assigned a dose number of 2, and the third observed vaccination is assigned a dose number of 3. Further observed doses are not counted within analyses. Vaccine doses must occur at least 3 days apart to be considered distinct doses.

AESI	Setting	Clean Window	Risk Window	Age Groups of Interest	Descriptive Monitoring	Sequential Testing
Anaphylaxis	IP, OP-ED	30 days*	0-1 day ^[19, 20]	6 m-4 y, 6 m-5 y	Yes	Yes
7 thaphylaxis	11,01 25	30 days	o i day	5-17 y, 6-17 y	Yes	Yes
Appendicitis	IP, OP-ED	365 days*	1-42 days ^[36,37]	6 m-4 y, 6 m-5 y	Yes	Yes
Appendicitis	11 , 01 - 20	303 days	1-42 day3	5-17 y, 6-17 y	Yes	Yes
Bell's Palsy / Facial	IP, OP, PB	183 days*		6 m-4 y, 6 m-5 y	Yes	Yes
Nerve Palsy	IP, OP, PB	165 days	1-42 uays 1	5-17 y, 6-17 y	Yes	Yes
Common Site	[Defined in		fo.41	6 m-4 y, 6 m-5 y	Yes	Yes
Thromboses with Thrombocytopenia	Footnote]**	365 days*	* 1-28 days ^[21]	5-17 y, 6-17 y	Yes	Yes
				6 m-4 y, 6 m-5 y	Yes	Yes
Deep Vein Thrombosis	IP, OP, PB	365 days* 1-28 days [25, 27]	5-17 y, 6-17 y	Yes	Yes	
Disseminated				6 m-4 y, 6 m-5 y	Yes	Yes
Intravascular Coagulation	IP, OP-ED	365 days*	365 days* 1-28 days ^[28]	5-17 y, 6-17 y	Yes	Yes
				6 m-4 y, 6 m-5 y	Yes	Yes
Encephalomyelitis	IP	183 days*	1-42 days ^[17]	5-17 y, 6-17 y	Yes	Yes
				6 m-4 y, 6 m-5 y	Yes	No
Febrile Seizures	IP, OP PB	42 days*	0-1 days	5-17y, 6-17 y	Yes	No
Guillain-Barre Syndrome	IP – Primary Position Only	365 days*	1-42 days [14,15]	6 m-4 y, 6 m-5 y	Yes	Yes
- Symulottic	T OSICION OTHY			5-17 y, 6-17 y	Yes	No
Hemorrhagic Stroke	IP	365 days*	1-28 days [40, 41]	6 m-4 y, 6 m-5 y	Yes	Yes
				5-17 y, 6-17 y	Yes	No
Immune	IP, OP, PB	365 days*	1-42 days [29, 30]	6 m-4 y, 6 m-5 y	Yes	Yes
Thrombocytopenia	-	,		5-17 y, 6-17 y	Yes	Yes
Kawasaki Disease	IP, OP, PB	365 days*	1-28 days	6 m-4 y, 6 m-5 y	Yes	No
210000	, 5.,5	202 34,5		5-17 y, 6-17 y	Yes	No

AESI	Setting	Clean Window	Risk Window	Age Groups of Interest	Descriptive Monitoring	Sequential Testing
Multisystem Inflammatory	IP, OP-ED	365 days*	1-42 days ^[16]	6 m-4 y, 6 m-5 y	Yes	No
Syndrome in Children		,		5-17 y, 6-17 y	Yes	No
Myocarditis / Pericarditis (All	IP, OP, PB	365 days* 1-7 days [12]	6 m-4 y, 6 m-5 y	Yes	Yes	
Settings) (1-7 day)		,		5-17 y, 6-17 y	Yes	Yes
Myocarditis / Pericarditis (All	IP, OP, PB	365 days*	365 days* 1-21 days [13]	6 m-4 y, 6 m-5 y	Yes	Yes
Settings) (1-21 day)	, ,	,		5-17 y, 6-17 y	Yes	Yes
Myocarditis / Pericarditis (IP/OP-ED)	IP, OP-ED	365 days*	vs* 1-7 days ^[12]	6 m-4 y, 6 m-5 y	Yes	Yes
(1-7 day)	,	,		5-17 y, 6-17 y	Yes	Yes
Myocarditis / Pericarditis (IP/OP-ED)	IP, OP-ED	365 days*	1-21 days ^[13]	6 m-4 y, 6 m-5 y	Yes	Yes
(1-21 day)	,	,	,	5-17 y, 6-17 y	Yes	Yes
Narcolepsy	IP, OP, PB	365 days* 1-42	365 days* 1-42 days [33-35]	6 m-4 y, 6 m-5 y	Yes	No
				5-17 y, 6-17 y	Yes	Yes
Non-Hemorrhagic Stroke	IP	365 days*	1-28 days [40, 41]	6 m-4 y, 6 m-5 y	Yes	Yes
Stroke				5-17 y, 6-17 y	Yes	Yes
Pulmonary Embolism	IP, OP, PB	365 days*	1-28 days ^[25-27]	6 m-4 y, 6 m-5 y	Yes	Yes
				5-17 y, 6-17 y	Yes	Yes
Seizures / Convulsions	IP, OP-ED	42 days*	0-7 days ^[23]	6 m-4 y, 6 m-5 y	Yes	Yes
				5-17 y, 6-17 y	Yes	Yes
Transverse Myelitis	IP, OP-ED	365 days*	1-42 days ^[18]	6 m-4 y, 6 m-5 y	Yes	No
				5-17 y, 6-17 y	Yes	No
Unusual Site Thromboses (Broad)	[Defined in	365 days*	1-28 days ^[22]	6 m-4 y, 6 m-5 y	Yes	No
with Thrombocytopenia	Footnote]**	303 udys	1-20 udy5 . 4	5-17 y, 6-17 y	Yes	No

Definitions: Clean Window is defined as an interval used to define incident outcomes where an individual enters the study cohort only if the AESI of interest did not occur during that interval. Risk Window is defined as an interval during which occurrence of the AESI of interest will be included in the analyses.

Setting Definitions: IP refers to inpatient facility claims. OP-ED refers to a subset of outpatient facility claims occurring in the emergency department. OP/PB refers to all outpatient facility claims, and professional/provider claims except those professional/provider claims with a laboratory place of service

- * References for this window could not be located in the literature and are instead based on input from FDA and external clinical experts.
- ** Both Common thromboses with thrombocytopenia and Unusual site thrombosis (broad) with thrombocytopenia are combined outcomes consisting of a thrombotic event (made up of other events such as acute myocardial infarction, deep vein thrombosis etc.,) and a thrombocytopenia event (defined in the IP, OP/PB setting). The overall setting definition for each outcome depends on individual setting definitions for each of these components Feasibility of sequential testing of certain outcomes in <5 age group may be further evaluated based on availability of background rates.

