The primary objective of the protocol addendum is to expand monitoring of the rates of AESI following COVID-19 vaccination among the pediatric population between the ages of 6 months and 17 years. The CBER BEST Workgroup will use the observed rates of the pediatric outcomes, as data accrue, to identify whether there is a potential increased risk of AESI following vaccination compared to a control baseline. Similar to the master protocol, the active safety monitoring in the pediatric population detailed in this protocol addendum is a method for signal detection and not signal evaluation. A statistically significant result does not necessarily indicate an increased risk of the adverse event in the pediatric population exposed to the vaccine; such a result must be further investigated and verified.

2. Overview

COVID-19 vaccinations are currently recommended for ages 6 months and older in the United States (US). The U.S. Food and Drug Administration (FDA) has authorized four COVID-19 vaccine brands through Emergency Use Authorization (EUA) or full FDA approval for different age groups, including:

- Pfizer-BioNTech (BNT162b2) COVID-19 Vaccine authorized in ages 6 months-15 years and approved in ages 16 years and older
- Moderna (mRNA-1273) COVID-19 Vaccine authorized in ages 6 months-17 years and approved in ages 18 years and older
- Janssen (Ad26.COV2.S) COVID-19 Vaccine authorized in ages 18 years and older
- Novavax (NVX-CoV2373) COVID-19 Vaccine authorized in ages 12 years and older

The authorized vaccinations in the pediatric population are summarized below by age group:

Table 1. Dosing Administration Schedule for EUA Authorizations

Brand	Age Group	Authorization	Date of Authorization
	6 months – 4 years	Three-dose primary series (3 micrograms)	EUA: 06/17/2022 ^[1]
		Two-dose primary series (10 micrograms)	EUA (primary series): 10/29/2021 ^[2]
	5-11 years	Third primary series dose for immunocompromised individuals (10 micrograms)	EUA (third dose): 01/03/2022 ^[2]
		Single booster at least 5 months after completion of primary series (10 micrograms)	EUA (single booster): 05/17/2022 ^[3]
		Two-dose primary series (30 micrograms)	EUA (primary series): 05/10/2021 ^[4]
		Third primary series dose for immunocompromised individuals (30 micrograms)	EUA (third dose): 08/12/2021 ^[5]
	12-15 years	First booster at least 5 months after completion of primary series (30 micrograms)	EUA (first booster): 01/03/2022 ^[6]

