As described in the primary protocol, claims databases have several advantages for use in vaccine surveillance. Claims databases constitute well-defined, large populations of millions of enrollees, whose healthcare service utilization is captured longitudinally across nearly all care settings. Claims databases also have disadvantages. The use of administrative codes, to some extent, limits the ability to accurately and reliably identify AESI. Moreover, the observation delay associated with claims data processing introduces bias in estimated risk. Further, some vaccinations for the pediatric population may not be billed to commercial insurance databases used in this study; therefore, the data may not be generalizable to the overall vaccinated pediatric population. The claims-based monitoring approaches outlined in this section are designed with these advantages and limitations in mind.

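### Numbering doses only by the order in which they are observed mislabels a dose whenever an earlier one is missed; this mainly biases the secondary dose-specific tests, not the pooled primary-series test.

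*Protocol*

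**What the plan says.** Footnote 2, called from Protocol Section 4.3 and printed in Section 4.4, gives the whole numbering rule: "Dose assignment is based on the chronological order in which vaccinations are observed for the person". It adds "Vaccine doses must occur at least 3 days apart to be considered distinct doses" and, for records after the third, "Further observed doses are not counted within analyses".

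Every exposure contrast rests on that number. The primary analysis is of the primary series. Footnote 1 says "For BNT162b2 in ages 5-17 and mRNA-1273, the primary series is defined as doses 1 and 2"; for BNT162b2 at 6 months to 4 years, "the primary series is defined as doses 1, 2 and 3". Section 4.3 continues: "the secondary analysis will focus on increased risk of AESI following specific doses (e.g., Dose 1, Dose 2, and boosters/third doses separately").

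Three other places bear on whether earlier doses are seen:
- Section 4 concedes that "some vaccinations for the pediatric population may not be billed to commercial insurance databases used in this study", and treats this only as a limit on generalizability.
- Section 3 describes IIS linkage as a way to improve capture, but says only that the databases may include such data.
- Section 4.1 requires continuous enrolment only from the start of the AESI-specific clean window. Table 3 sets that window at 30 days for anaphylaxis, 42 days for seizures, 183 days for Bell's palsy and encephalomyelitis, and 365 days for most other outcomes.

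**The concern.** Observed order equals true order only if every earlier dose was captured, and the protocol itself says capture is incomplete. When dose 1 is missing, the child's true dose 2 is analysed as dose 1. In BNT162b2 at ages 5-17 years, where Table 1 lists boosters, the booster is then analysed as dose 2 and so enters the primary series.

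An error in the other direction is possible. If one dose has two records dated 3 or more days apart, the second record becomes dose 2, the true dose 2 becomes dose 3 and goes to the booster/third-dose test, and a true booster becomes number 4 and is dropped. Because Section 4.1 censors at a following dose, the false dose also cuts short the true dose's risk window.

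At stake is which dose a signal is attributed to, which is what the dose-specific tests are meant to show.

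**Working it through.** The protocol states no capture rate, duplicate rate or misclassification figure, so there is nothing of its own to reproduce. The rule in footnote 2 was applied by enumeration to BNT162b2 at ages 5-17 years.

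Input from the document: booster uptake b = 0.30, borrowed from the planning assumption in Section 4.6.1 (there it applies to eligible persons). Assumptions: everyone receives two primary doses; each dose is captured independently with probability c; person-time per labelled dose is equal; true rate ratios (RR) are 1, 5 and 1 for dose 1, dose 2 and booster.

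**Missing records.** Doses per person under each label:
- Labelled dose 1: true dose 1, c; true dose 2, c(1-c); booster, bc(1-c)².
- Labelled dose 2: true dose 2, c²; booster, 2bc²(1-c).

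At c = 0.80:
- Dose-1 RR = (0.80×1 + 0.16×5 + 0.0096×1) / 0.9696 = 1.66.
- Dose-2 RR = (0.64×5 + 0.0768×1) / 0.7168 = 4.57.
- Primary-series RR = (1.6096 + 3.2768) / (0.9696 + 0.7168) = 2.90, against 3.00 with full capture.
- Booster share of the primary series = (0.0096 + 0.0768) / 1.6864 = 5.1%.

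| Assumed capture c | 95% | 90% | 80% |
|---|---|---|---|
| Dose-1 labels that are not true dose 1 | 5% | 9% | 17% |
| Captured boosters placed in primary series (1-c²) | 10% | 19% | 36% |
| Booster share of primary-series doses | 1.4% | 2.8% | 5.1% |
| Dose-1 RR (true 1) | 1.19 | 1.36 | 1.66 |
| Dose-2 RR (true 5) | 4.88 | 4.77 | 4.57 |
| Primary-series RR (true 3.00) | 2.97 | 2.94 | 2.90 |

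**Before boosters exist (b = 0).** The dose-1 RR is (6-5c)/(2-c), again 1.19, 1.36 and 1.67. The primary-series RR is (c + 5c)/(2c) = 3.00 at any c. The dose-1 error does not need boosters; the primary-series error does.

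**Timing.** Section 4.2 start dates against Table 1 booster authorizations: ages 5-11, 10/29/2021 and 05/17/2022; ages 12-15, 05/10/2021 and 01/03/2022; ages 16-17, 12/11/2020 and 12/9/2021. Each gap exceeds 6 months, the period from which surveillance length is derived.

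**Duplicates.** Take c = 1 and an assumed probability d of a second record 3 or more days later but before the next dose, with the false record carrying RR 1. Labelled dose 3 contains true dose 2 (d), a false record of dose 2 (d(1-d)) and booster (b(1-d)²). At d = 0.05 the dose-3 RR is (0.05×5 + 0.0475 + 0.27075) / 0.36825 = 1.54, and 0.0975/0.36825 = 26% of dose-3 labels are not true boosters. At d = 0.02 these are 1.24 and 12%.

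**The case against.** The strongest reply is that the primary analysis pools doses 1 and 2, so a swap between them cancels. Only a booster coming in or a true dose 2 going out matters, and the table shows how little that moves the result. Booster leakage also concerns mainly BNT162b2 at ages 5-17 years: Table 1 lists no monovalent booster for mRNA-1273 or NVX-CoV2373, and at 6 months to 4 years the third BNT162b2 dose is itself primary series. The planned 6 months precede every BNT162b2 booster authorization, although the limit is an event count and may run longer in calendar time. All of this stands, and a reader who infers that the primary analysis is seriously compromised goes too far.

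Other points stand in part. IIS linkage reduces missed doses. Missingness may cluster in children none of whose doses are billed; they are absent rather than mislabelled, so independent capture may overstate the error. A 365-day clean window secures long look-back, so short enrolment is an issue mainly for anaphylaxis and seizures; non-billing affects all outcomes. The dose-specific tests are secondary, and Section 1 requires any signal to be investigated further.

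Three stronger inferences are not supported:
- That a harmless dose 1 would cross the null. Section 4.6.1 sets the null at 1+m; a Table 5 entry of 1.25 read as m gives 2.25, above every dose-1 value here. Read as a null rate ratio it gives 1.25, which 1.36 exceeds. The conclusion depends on the reading.
- That the Table 1 interval ("Single booster at least 5 months after completion of primary series") would sort out all mislabelled doses. A dose 2 with no earlier observed record has no interval to test, and the interval does not identify duplicates.
- That discordant duplicates occur. They are plausible when claims and IIS records are combined, but the document reports none, and the 3-day rule is itself a de-duplication rule.

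**Conclusion.** The concern holds for the secondary dose-specific tests. The rule is fixed in the protocol text, and its premise of complete capture is contradicted by Section 4. Under assumed true rate ratios of 1, 5 and 1 and independent capture of 95%, 90% and 80%, a dose with no effect shows a rate ratio of about 1.19, 1.36 and 1.66. The size in practice is unknown, since neither capture nor the true effects are given. The pooled primary-series test is little affected (2.90 against 3.00 at 80% capture), and less so before boosters were available. The duplicate route is a plausible addition and carries less weight. The change is worth making because it is inexpensive and protects the attribution of a signal to a dose.

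**What to change.** In footnote 2, take the dose number from the product code or IIS record where it carries one, and keep observed order as the fallback.

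Repeat the dose-specific tests, and the primary-series test for BNT162b2 at ages 5-17 years, as sensitivity analyses:
- (a) in IIS-linked members enrolled since their age group's study start date;
- (b) with an observed dose 5 months or more after the previous observed dose treated as a booster, for series whose Table 1 entry has that interval;
- (c) with a de-duplication gap longer than 3 days.

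These are analysis labels only and change nothing in vaccination practice. The cost is more programming on data already held, smaller numbers in (a), and some late second doses labelled as boosters in (b). The protocol does not say how often its codes carry a dose number, so the gain from the first step cannot be judged in advance; (b) cannot recover a dose 2 whose dose 1 was never observed, which is why (a) is needed.

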4.5 Descriptive Analyses

As in the master protocol, we will use similar descriptive statistics to summarize the observed rates of AESI in the pediatric population. Table 3 lists all the AESI for which we will be conducting descriptive monitoring only. These statistics will be stratified by age group³, sex, region, urban/rural status, and data source. Descriptive statistics will be updated continuously, synchronized with the sequential testing, on a monthly basis, as allowed by the individual data source. Table 4 represents the proposed (observed) descriptive statistics for the pediatric population.

Table 4. Example Table of Descriptive Statistics

	All Doses*				
Patient Characteristic	# of COVID-19	Observed (Outcomes – [Outcome]		
	Vaccinations	#	Rate (per 100k person-years)		
Total	No data	No data	No data		
Sex	No data	No data	No data		
Female					
Male					
Age (years)	No data	No data	No data		
5-11					
12-15					
16-17					
Urban/Rural	No data	No data	No data		
Urban					
Rural					

³ For BNT162b2, the age groups will be: 6 months-4 years, 5-11 years, 12-15 years, and 16-17 years For mRNA-1273, the age groups will be: 6 months-5 years, 6-11 years, 12-15 years, and 16-17 years. For NVX-CoV2373, the age groups will be: 12-15 years and 16-17 years. For the "all brand" descriptive statistics, the age stratifications for BNT162b2 will be used where applicable.

	All Doses*			
Patient Characteristic	# of COVID-19	Observed Outcomes – [Outcome]		
	Vaccinations	#	Rate (per 100k person-years)	
HHS Region	No data	No data	No data	
[Region 1]				
[Region 2]				
[Region 3]				
[Region 4]				
[Region 5]				
[Region 6]				
[Region 7]				
[Region 8]				
[Region 9]				
[Region 10]				
Facility/Provider Type	No data	No data	No data	
Hospital				
Office				
Pharmacy				
Skilled Nursing Facility				
Home Health Agency				
Mass Immunization Center				
Others				

^{*} Additional statistics will be provided by individual doses

Note: Separate tables will be provided for each Data Partner.

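### Febrile seizures are the only day-0 outcome counted in all outpatient and professional claims, so a past seizure coded at the vaccination visit may enter the descriptive rate

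*Protocol*

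**What the plan says.** The Table 3 entry in protocol section 4.4 reads "Febrile Seizures IP, OP PB 42 days* 0-1 days". Descriptive monitoring is marked yes and sequential testing no in both age rows.

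The note under the table explains the settings. For the wide one, "OP/PB refers to all outpatient facility claims, and professional/provider claims except those professional/provider claims with a laboratory place of service". For the narrow one, "OP-ED refers to a subset of outpatient facility claims occurring in the emergency department".

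The same note says what counts as an event: "Risk Window is defined as an interval during which occurrence of the AESI of interest will be included in the analyses". It also says what the clean window does: "an individual enters the study cohort only if the AESI of interest did not occur during that interval".

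Section 4.3 finds vaccinations in claims through product codes "in the professional, outpatient institutional, inpatient, or prescription drug care settings", and also through immunization registry (IIS) records.

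**The concern.** For a dose billed at an office or clinic visit, the visit's own claim lies in a setting where febrile seizures are counted, and it is dated day 0, inside the risk window. If that claim also carries a febrile seizure diagnosis for an episode that happened months earlier, nothing in section 4.4 separates it from a new seizure. The clean window removes only children with such a code in the previous 42 days.

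The date of this visit is set by the vaccination itself, so any coding habit tied to visits is concentrated on day 0. That is also a day on which the chosen window looks for true events.

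What is at stake is how the febrile seizure rate is read. The outcome has no sequential test, so the descriptive rate is its only dedicated output.

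**Working it through.** **Step 1. Is the combination unique?** Table 3 lists 24 outcomes, counting the four myocarditis/pericarditis definitions separately.

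| Outcome with day 0 in the risk window | Window | Clean window | Setting |
|---|---|---|---|
| Anaphylaxis | 0-1 | 30 days | IP, OP-ED |
| Seizures/convulsions | 0-7 | 42 days | IP, OP-ED |
| Febrile seizures | 0-1 | 42 days | IP, OP, PB |

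Nine outcomes use IP, OP and PB: Bell's palsy, deep vein thrombosis, febrile seizures, immune thrombocytopenia, Kawasaki disease, the two all-settings myocarditis/pericarditis outcomes, narcolepsy and pulmonary embolism. Eight of them start at day 1. The two thrombosis-with-thrombocytopenia outcomes, whose settings are defined by footnote, also start at day 1. The overlap of day 0 with OP/PB is febrile seizures alone.

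**Step 2. Does the protocol text block a non-incident code?** The only setting exclusion is professional claims with a laboratory place of service. Table 3 states no same-day rule and no diagnosis-position rule for febrile seizures, although it does state a position rule for Guillain-Barré syndrome. An episode coded more than 42 days earlier passes the clean window. No code list is shown, so it is unknown whether a pure history code would qualify. The clearer route is an active febrile seizure code used for a past episode.

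**Step 3. How sensitive is the rate?** The protocol states no febrile seizure rate, so there is no figure of its own to reproduce. Table 4 expresses rates per 100,000 person-years.

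- Person-years from 100,000 doses with complete two-day follow-up: 100,000 × 2 / 365.25 = 547.6.
- Added rate for k non-incident day-0 codes per 100,000 doses: k / 547.6 × 100,000 = 182.6 × k.

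The value of k is an assumption, because the documents give none:

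| Assumed k per 100,000 doses | Added rate per 100,000 person-years |
|---|---|
| 0.1 | 18 |
| 1 | 183 |
| 5 | 913 |
| 10 | 1,826 |

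Here k is averaged over all doses in the denominator, including those with no visit claim.

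**The case against.** **A reader might infer that the rate is certainly inflated.** The documents do not support that. They show neither the code list nor how often past febrile seizures are coded at vaccination visits. Code lists and similar rules are commonly kept outside a protocol, so their absence is not itself a fault. What stands is that setting and window are fixed in Table 3, and together they leave the route open.

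**A reader might also want a multiple of the true rate.** That needs a background incidence, which the documents do not give. With assumed incidences of 300 to 1,500 per 100,000 person-years, the factor 1 + 182.6k / incidence is about 1.01 to 1.06 at k = 0.1 and about 3.4 to 13 at k = 20. A range that wide says nothing about the actual size.

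**Not every dose is exposed.** Some doses are identified from prescription drug claims or registry records, and the protocol notes that some are not billed to these insurers at all. Where there is no visit claim the mechanism does not operate. This dilutes the effect but does not remove it.

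**The consequence is limited.** Febrile seizures are not tested sequentially and have no margin in Table 5, so no false PMaxSPRT signal can result. It would also be too strong to say that the rate cannot be compared with any background rate: the background rates protocol is not at hand, and a rate built with the same setting may help. Section 4 concedes that "The use of administrative codes, to some extent, limits the ability to accurately and reliably identify AESI". That is a general caution and does not address this day-0 route.

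**The wide setting may be deliberate.** Broad capture for a descriptive outcome and narrow capture for the tested seizures/convulsions outcome is a coherent choice. Dropping all day-0 OP/PB claims would lose true events treated in an office or visible only on a professional claim. This objection stands, and it argues for showing both versions rather than restricting the existing one.

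**Conclusion.** The point holds as a risk of unknown size. Febrile seizures are the only Table 3 outcome that joins day 0 to all outpatient and professional claims, and the protocol gives no reason for the exception. Read as written, a past febrile seizure coded at the vaccination visit may be counted as a day-0 event if none was coded in the previous 42 days.

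The one size that can be stated is the sensitivity: about 183 per 100,000 person-years for each such code per 100,000 doses, assuming complete two-day follow-up. The effect is limited to descriptive monitoring and to doses billed at a visit.

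**What to change.** In Tables 3 and 4, report febrile seizures twice: in all settings, as now, and in IP/OP-ED only. Table 3 already does this for myocarditis/pericarditis. Show day 0 and day 1 separately in both versions, and apply the same setting to any background rate shown beside them.

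A day-0 excess that appears in all settings but not in IP/OP-ED would point to visit coding or to seizures managed only in an office. Either way, the reader sees how much of the rate depends on those claims.

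The cost is a few extra descriptive rows with small counts. No true event is dropped, because the all-settings rate is kept.
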